£ PD: Carfilzomib proteasome chymotrypsin-like activity in PBMC (LMP7 and b5 activity) and gamma-H2AX and Topoisomerase-I expression Day 1: The sampling times relative to the start of irinotecan infusion: Pre-irinotecan, 90 min, 2 hours, 5.5 hours; Day 2: pre-carfilzomib infusion

& Submit tumor block or 10 unstained slides of pre-existing tumor

@ Follow-up will be for 30 days after last treatment or until all drug-associated (possible, probably or definite) toxicities have resolved to Grade 1 or less

Phase II Study Calendar:

Required Studies		Cycle 1				Cycle 2,4,6					Cycle 3, 5											
-			Day Day																			
	Screen within 2 weeks unless specified	1	2	8	9	15	16	1	2	8	9	15	16	22	1	2	8	9	15	16	Off study	$Follow-up^{@}$
PHYSICAL																						
Informed Consent	X																					
Medical History	Х																					
Physical Examination	X							Х							Х						Х	Х
Performance Status and Weight	Х							Х							Х						Х	Х
Toxicity Assessment								Х							Х						Х	Х
Disease Assessment	X							Х							Х							
RADIOLOGY																						
CT/MRI scan ¶	Х													Х							Х	Х
Brain CT/MRI #	Х																					
ECG#	X																					
LABORATORY																						
CBC w/differential	X*	Х		Х		х		Х		Х		Х			Х		Х		Х		Х	Х
Serum chemistries §	X*	Х		Х		Х		Х		Х		Х			Х		Х		Х		Х	Х
Serum Magnesium	X*	Х						Х							Х						Х	Х
Serum or urine Pregnancy Test	X*																					
TREATMENT																						
Irinotecan √		Х		Х		Х		Х		Х		Х			Х		Х		Х			
Carfilzomib $$ (study provided)		Х	Х	Х	Х	х	Х	Х	Х	Х	х	Х	Х		Х	Х	Х	Х	Х	Х		
Dexamethasone 8 mg		Х	Х	Х	Х	Х	Х															
PK/PD/Correlative																						
Pharmcodynamic blood tests £		X	Х																			
Tissue Submission &	X			1				1		1					1			1				ĺ

¶ CT or MRI (the same method used at prestudy to meet the eligibility criteria in Section 5.3) must be repeated after ever two cycles of treatment until disease progression. Once off study, the frequency of this scan may be reduced to every 3 months until disease progression.

#Prestudy, and then as clinically indicated

* This test is required prestudy within 2 weeks of starting study medication.

§ Sodium, potassium, calcium, chloride, , creatinine, magnesium, SGOT, , alkaline phosphatase, total bilirubin prior to treatment on Day 1 of each cycle (at most 2 days prior to Day 1 of the next cycle); Sodium, potassium, chloride, creatinine, prior to treatment on Day 8 & 15

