11.3 PLANNED METHODS OF ANALYSIS

Six month survival and progression free survival rates, as well as response to treatment, will be calculated based on all subjects who receive the recommended Phase II dose of the drug combination. All eligible subjects accrued to phase II who have received at least one dose of each drug in the regimen will be considered as evaluable in the phase II analysis.

Survival will be estimated using the Kaplan-Meier method, separately for each stratum. Response and progression will be determined according to RECIST criteria. Overall survival is defined as the time between registration and death due to any cause. Subjects last known to be alive are censored at date of last contact. Progression free survival is defined as the date of registration to the date of first documentation of progression, or death due to any cause. Subjects last known to be alive and progression free are censored at the date of last contact. Due to the limited sample size in a Phase II setting, correlative studies will be considered exploratory in nature and will be used to formulate hypotheses that can be tested using correlative data from a Phase III setting.

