- d. Progression: One or more of the following must occur: 20% increase in the sum of appropriate diameters of target measurable lesions over smallest sum observed (over baseline if no decrease during therapy) using the same techniques as baseline, as well as an absolute increase of at least 0.5 cm. Unequivocal progression of non-measurable disease in the opinion of the treating physician (an explanation must be provided). Appearance of any new lesion/site. Death due to disease without prior documentation of progression and without symptomatic deterioration (see 10.2e).

Notes regarding new lesions: FDG-PET imaging can complement regular scans in identifying new lesions according to the following algorithm.

1) Negative FDG-PET at baseline, with a positive FDG-PET at follow-up is a sign of progression based on a new lesion.

2) No FDG-PET at baseline and a positive FDG-PET at follow-up corresponding to a potential new site of disease must have a confirmation by anatomical assessment (e.g. CT, MRI, x-ray) as new site of disease to be considered progressive disease. In such a case, the date of progressive disease will be the date of the initial abnormal FDG-PET.

- e. Symptomatic deterioration: Global deterioration of health status requiring discontinuation of treatment without objective evidence of progression. Efforts should be made to obtain objective evidence of progression after discontinuation.
- f. Assessment inadequate, objective status unknown. Progression or symptomatic deterioration has not been documented, and one or more target measurable lesions have not been assessed or inconsistent assessment methods were used.
- g. Objective status notes:
 - 1. "Appropriate diameters" means short axis for lymph nodes; longest diameters for all other lesions,
 - 2. An objective status of PR or stable cannot follow one of CR. Stable can follow PR only in the rare case that tumor increases too little to qualify as progression, but enough that a previously documented 30% decrease no longer holds.
 - 3. In cases for which initial flare reaction is possible (hypercalcemia, increased bone pain, erythema of skin lesions), objective status is not progression unless either symptoms persist beyond 4 weeks or there is additional evidence of progression.
 - 4. Lesions that appear to increase in size due to presence of necrotic tissue will not be considered to have progressed.

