- 1 Restricted in physically strenuous activity but ambulatory and able to carry out work of a light or sedentary nature, e.g., light housework, office work.
- 2 Ambulatory and capable of self-care but unable to carry out any work activities; up and about more than 50% of waking hours.
- 3 Capable of limited self-care, confined to bed or chair more than 50% of waking hours.
- 4 Completely disabled; cannot carry on any self-care; totally confined to bed or chair.

5. **Progression-Free Survival** From the date of registration to first documentation of progression or symptomatic deterioration (as defined in 2.d and 2.e), or death due to any cause. Subjects last known to be alive and progression-free are censored at date of last contact.

6. **Overall Survival** From the date of registration to the date of death due to any cause. Subjects last known to be alive are censored at date of last contact.

7. Time to Treatment Failure From date of registration to date of first observation of progressive disease (as defined in 2.d), death due to any cause, symptomatic deterioration (as defined in 2.e), or early discontinuation of treatment.

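### PFS is censored at last contact, not at the last tumor assessment, so six-month PFS can be modestly overstated if subjects stop scanning while still in contact (Section 11.3, Appendix B item 5)

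*Combined protocol and SAP*

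**What the plan says.** Section 11.3 makes PFS rates a reported output: "Six month survival and progression free survival rates, as well as response to treatment, will be calculated". It states that "Response and progression will be determined according to RECIST criteria", and its PFS censoring rule is "Subjects last known to be alive and progression free are censored at the date of last contact". Appendix B item 5 agrees: "Subjects last known to be alive and progression-free are censored at date of last contact". Both places use the same date to censor overall survival. Neither mentions the last tumor assessment, and no rule covers missed scans.

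The Phase II calendar in Section 7 puts CT or MRI after every two cycles until progression, in the Day 22 column of cycles 2, 4 and 6. It marks further scans off study and in follow-up, with a footnote on their spacing: "Once off study, the frequency of this scan may be reduced to every 3 months until disease progression". Follow-up contact is also every 3 months. Under Section 8.2 it ends at 2 years, death or study closure, whichever comes first.

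Appendix B item 2.f treats a subject's status as unknown when target lesions were not assessed. Section 11 lists PFS as a secondary endpoint. The primary endpoint is the proportion alive at six months.

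**The concern.** Last contact is the right censoring date for overall survival, because a contact establishes that the subject is alive. It does not establish RECIST status. Section 8.1 lets treatment end for toxicity, delay, physician discretion or withdrawal. A subject who leaves that way, stops scanning and still answers three-monthly contacts can be carried as progression-free over months without a tumor measurement. Appendix B item 2.f would call the status unknown over that same interval.

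At stake is a named secondary endpoint in a single-arm trial. Against last-scan censoring, the difference can only favor the regimen.

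**Working it through.** **1. The plan's own figures.** The documents give no PFS figure. The nearest ones reproduce, and none uses the PFS rule:
- Sensitive stratum, at least 22 of 40 alive, 40% against 60%: exact binomial alpha .0392 and power 79.1% (plan: .04 and 79%).
- Refractory stratum, at least 15 of 40 alive, 25% against 45%: alpha .0544 and power 86.7% (plan: .054 and 86%).
- Precision: 1.96 × √(.25/40) = .155 (plan: at most ±16%).

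**2. Direction.** Assume Kaplan-Meier for PFS, which Section 11.3 names for survival: S(t) = ∏(1 − d/n) over event times up to t. With the same events under both rules, d is the same. Last-contact censoring keeps subjects at risk longer, so each n is at least as large. Each factor, and so S(t), is therefore at least as high. A subject who stops scanning and later dies within follow-up is an event at death under either rule. The rules differ only for subjects still alive at the cut with no documented progression.

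**3. Inputs for the size.**
- Scan days from the calendar: 28 × (c − 1) + 22 for c = 2, 4, 6 gives 50, 106 and 162, then every 91 days.
- Assumed: exponential time to progression, median 60, 90 or 120 days; median 120 days from progression to death; death without progression with median about 12 months.
- Assumed: a share f stop scanning after 0, 1 or 2 scans but stay in contact.
- Six months is 182.6 days; 20,000 subjects per scenario.
- Follow-up is either the full 730 days or uniform over 183 to 730 days. The second is a cut 6 months after the last registration with (730 − 183)/30.4 = 18 months of accrual, the lower end of Section 3.3.

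**4. Results.** Six-month PFS in %, last contact / last scan, with the difference in points:

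| Median (days) | f | Cut 6 months after last registration | Full 2 years |
|---|---|---|---|
| 60 | 0 | 10.9 / 10.8 (0.1) | 10.6 / 10.6 (0.0) |
| 60 | 10% | 13.3 / 12.4 (0.9) | 13.0 / 12.9 (0.1) |
| 60 | 30% | 17.7 / 15.2 (2.5) | 17.4 / 17.1 (0.3) |
| 90 | 0 | 19.9 / 19.8 (0.1) | 20.3 / 20.3 (0.0) |
| 90 | 10% | 22.5 / 21.5 (1.0) | 22.4 / 22.2 (0.2) |
| 90 | 30% | 26.4 / 23.6 (2.8) | 26.6 / 26.1 (0.5) |
| 120 | 0 | 28.0 / 27.9 (0.1) | 28.0 / 28.0 (0.0) |
| 120 | 10% | 29.9 / 28.7 (1.2) | 30.0 / 29.8 (0.2) |
| 120 | 30% | 33.1 / 29.9 (3.2) | 32.9 / 32.4 (0.5) |

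**5. Other assumptions.** A second simulation used a median of 13.3 weeks to progression (the topotecan figure in Section 1.5), 8-weekly scans for 24 weeks and then 3-monthly, and 20-month accrual. Complete scanning gave about 24%. With 10/20/30% stopping at random and a cut 6 months after the last registration, last contact exceeded this by 1.7/3.4/5.1 points and last scan by 0.9/2.1/3.1. The differences between rules are 1.7 − 0.9 = 0.8, 3.4 − 2.1 = 1.3 and 5.1 − 3.1 = 2.0. Further runs gave about 0.6 to 1.7 points if scanning stops at progression, and about 0.1 to 0.6 with full 2-year follow-up.

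**6. What last-scan censoring leaves.** In step 5, 3.1 of the 5.1 points remain at 30%. In the step 3 model (median 90 days, f = 20%, cut 6 months after last registration), the rates are 24.2% by last contact, 22.2% by last scan and 17.4% true. The change of rule removes 24.2 − 22.2 = 2.0 of the 24.2 − 17.4 = 6.8 points. The other 4.8 come from late or missed detection.

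**7. Scale.** One subject in 40 is 2.5 points. At a PFS rate of 24%, the half-width is 1.96 × √(.24 × .76/40) = .132, or about 13 points.

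**The case against.** The strongest defense is that contact without a scan departs from the plan. The calendar schedules scans until progression, off study as well, at the same 3-month interval as contact. If sites comply, the rules agree to within 0.1 points in step 4. This stands, and it is why the point is conditional.

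The rule also covers only subjects known to be progression-free, so it need not mean a contact of any kind. That stands in part, because the text does not say how status is known without a scan. It matters. If every progression among those who stop scanning were recognized at the next 3-monthly contact (median 90 days, 30% stopping, cut 6 months after last registration), last contact gives 19.4% and last scan 18.0%. Complete scanning gives 19.9%, so last contact would then be the closer of the two to it. Two analysts could read the rule differently, which is itself a reason to state the date.

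A reader might infer that subjects with symptomatic deterioration ("Global deterioration of health status requiring discontinuation of treatment without objective evidence of progression") are carried as progression-free. Appendix B item 5 does not support that: its PFS runs "to first documentation of progression or symptomatic deterioration (as defined in 2.d and 2.e), or death due to any cause", so they are events there. Section 11.3 omits that event ("Progression free survival is defined as the date of registration to the date of first documentation of progression, or death due to any cause"), but that is a conflict over the event definition, separate from the censoring date.

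A reader might also infer larger effects from a cut soon after the last registration. That cannot be the final analysis, because the primary endpoint needs six-month status on every subject, and the interim look in Section 11.2 tests survival, not PFS.

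**Conclusion.** The point holds as a minor, conditional one. Both places name a censoring date that is not tied to evidence about progression. If 10 to 30% of subjects stop scanning while in contact, six-month PFS is about 1 to 3 points higher under last-contact than under last-scan censoring, with a cut 6 months after the last registration. With full 2-year follow-up the difference is about 0.6 points or less. If scans follow the calendar it is near zero. These sizes rest on an assumed stopping rate, exponential times and Kaplan-Meier estimation, since the documents give no missed-scan rate.

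Two stronger readings are tempting. One is that six-month PFS is overstated as a matter of course; the documents do not support this, because the effect needs missed scans and incomplete follow-up. The other is that changing the date removes the bias; it removes only part, because progression nobody detected stays undetected under either rule.

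The effect is at most about one subject per stratum and well inside the sampling error. PFS has no benchmark or test in Section 11, and the primary endpoint and its decision rules are unaffected.

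**What to change.** In Section 11.3 and Appendix B item 5, censor PFS at the date of the last adequate tumor assessment that showed no progression, or at registration if there is none. Keep last-contact censoring for overall survival. Report the last-contact version of PFS as a sensitivity analysis, so that any gap between the two is visible.

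This changes analysis wording only and uses scan dates the trial already collects. The cost is slightly less follow-up time and a slightly wider interval for PFS.

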12 INVESTIGATIONAL PRODUCT

12.1 CARFILZOMIB DESCRIPTION

Carfilzomib is a synthetic small molecule peptide bearing the chemical name (2S)-N-((S)-1-((S)-4-methyl-1-((R)-2-methyloxiran-2-yl)-1-oxopentan-2-ylcarbamoyl)-2-phenylethyl)-2-((S)-2-(2-morpholinoacetamido)-4-phenylbutanamido)-4-methylpentanamide. The molecular formula is C₄₀H₅₇N₅O₇ and the molecular weight is 719.91. It specifically functions as an inhibitor of the chymotrypsin-like activity of the 20S proteasome which leads to the accumulation of protein substrates within the cell and induction of apoptosis.

12.1.1 FORMULATION

Carfilzomib for Injection is supplied as an individually cartooned single-use vial containing a dose of 60 mg of Carfilzomib as a white to off-white lyophilized cake or powder. When reconstituted, Carfilzomib contains 2 mg/mL isotonic solution of carfilzomib, 100 mg/mL sulfobutylether-beta-cyclodextrin, and 1.9 mg/mL citrate buffer (pH 3 to 4). Each mL of reconstituted drug product contains 0.3 mmol (7 mg) of sodium.

12.1.2 STORAGE

Lyophilized Carfilzomib for Injection must be stored at 2°C to 8°C under the conditions outlined in the separate Pharmacy Manual, in a securely locked area to which access is limited to appropriate study personnel.

12.1.3 RECONSTITUTION AND ADMINISTRATION

Aseptically reconstitute each vial of carfilzomib by slowly injecting 29 ml Sterile Water for Injection, USP, directing the solution onto the inside wall of the vial to minimize foaming. Gently swirl and/or invert the vial slowly for about 1 minute, or until complete dissolution of any cake or powder occurs. Do not shake to avoid foam generation. If foaming occurs, allow solution to rest in the vial for about 2 to 5 minutes, until foaming subsides. After reconstitution, carfilzomib is ready for intravenous administration. The reconstituted product should be a clear, colorless solution. If any discoloration or particulate matter is observed, do not use the reconstituted product.

When administering in an intravenous back, withdraw the calculated dose from the vial and dilute into 50 ml to 100 mL 5% Dextrose Injection, USP intravenous bag. Immediately discard the vial containing the unused portion. The reconstituted solution contains carfilzomib at a concentration of 2 mg/ml and is stable at room temperature for four hours (or 24 hours at $2^{\circ}C$ – to $8^{\circ}C$) following reconstitution.

The IV administration line should be flushed with normal saline or 5% Dextrose Injection, USP immediately before and after carfilzomib administration. Carfilzomib should not be administered as a bolus.

12.1.4 ACCOUNTABILITY

Amgen, and the Investigator will maintain records of each shipment of investigational product. The records will document shipment dates, method of shipment, batch numbers, and quantity of vials contained in the shipment. Upon receipt of the investigational product, the designated recipient at the study site will inspect the shipment, verify the number and condition of the vials, and prepare an inventory or drug accountability record.

Drug accountability records must be readily available for inspection by representatives of Amgen and by regulatory authorities.

Empty and partially used vials should be accounted for and destroyed at the study site in accordance with the internal standard operating procedures. Drug destruction records must be readily available for inspection by representatives of Amgen and by regulatory authorities.

Only sites that cannot destroy unused drug on-site will be required to return their unused supply of investigational product.

12.1.5 CARFILZOMIB DRUG ORDERING

Carfilzomib will be provided by Amgen. Investigators must order carfilzomib by accessing a password protected online, secure website. Amgen will provide access information to the system for all appropriate study personnel after the requirements for study activation at the site

have been confirmed. Please see below for requirements prior to submitting the initial drug request.

An initial startup supply for the first cycle may be ordered prior to subject registration.

Prior to submitting the initial drug request, investigators must first do the following:

- Be aware that investigational new drug regulatory best practices mandate that drug must be shipped to the single designated pharmacy listed in Box 3 of the FDA-1572 Form; further dispensation to satellite pharmacies will be the site Principal Investigator's responsibility. Compliance with Good Clinical Practices for drug accountability, storage, dispensation, and documentation is expected.
- 2. Prior to the submission of the initial drug request, the site investigator must confirm the required regulatory documents have been submitted to the CRAB CTC Operations Office at the time of site activation. Documents to be submitted include: site/central IRB approved Informed Consent and site/central IRB approval letter for current version of the protocol and informed consent form. Once completed documents have been received, the CRAB CTC Operations Office will forward the documents to Amgen prior to the site's initial drug request.

12.2 IRINOTECAN

12.2.1 IRINOTECAN DESCRIPTION

Irinotecan hydrochloride injection is an antineoplastic agent of the topoisomerase I inhibitor class. Irinotecan hydrochloride was clinically investigated as CPT-11. Irinotecan hydrochloride is a semisynthetic derivative of camptothecin, an alkaloid extract from plants such as Mappia foetida and Camptotheca acuminata. The chemical name is (S) - [CPT-11, (4S)-4, 11- diethyl-4-hydroxy-9-

[(4-piperidinopiperidino) carbonyloxy] -IHpyroano [3',4':6, 7l indolzino [1,2-bl quino line-3, 14(4H, l2H) dione hydrochloride trihydrate]

12.2.2 FORMULATION

Irinotecan hydrochloride injection is supplied as a sterile, pale yellow, clear, aqueous solution. It is available in two single-dose sizes: 2 mL-fill vials containing 40 mg Irinotecan hydrochloride, and 5 mL-fill vials containing 100 mg irinotecan hydrochloride. Each milliliter of solution contains 20 mg of irinotecan hydrochloride (on the basis of the trihydrate salt), 45 mg of sorbitol NF powder, and 0.9 mg of lactic acid, USP. The pH of the solution has been adjusted to 3.5 (range, 3.0 to 3.8) with sodium hydroxide or hydrochloric acid. Irinotecan hydrochloride injection is intended for dilution with 5% Dextrose Injection, USP (D5W), or 0.9% Sodium Chloride Injection, USP, prior to intravenous infusion. The preferred diluent is 5% Dextrose Injection, USP.

12.2.3 TOXICOLOGY

Human Toxicity: Virtually all Phase I and II studies of irinotecan have reported neutropenia and diarrhea as the dose-limiting toxicities. It is expected that these toxicities will also be encountered in this trial. Other Grade 2-3 toxicities seen include nausea and vomiting, anorexia, abdominal cramping, cumulative asthenia, thrombocytopenia, renal insufficiency, increase in transaminase level and hair loss. Sporadic cases of pulmonary toxicity, manifested as shortness of breath and nonproductive cough, have also been reported.

12.2.4 PHARMACOLOGY

Pharmacokinetics: Several studies describing the pharmacokinetic characteristics of irinotecan (CPT-11) and its active metabolite, SN-38, when administered alone or in combination with other agents (including cisplatin) in subjects with small cell or non-small cell lung cancer have been reported in published literature. CPT- 11 is converted by carboxylesterases to its more active metabolite, SN-38. In vitro, SN-38 is 250 to 1,000 fold more potent than CPT-11 in the inhibition of topoisomerase I activity. A reversible, pH-dependent hydrolysis converts the closed lactone E ring form of both CPT-11 and SN-38 to the open, carboxylate form of each

Confidential

compound. Only the closed ring (lactone) forms of CPT-11 and SN-38 are effective topoisomerase I inhibitors. The mean terminal half-life of SN-38 in plasma is slightly longer than that for CPT-11; 11.5 ± 3.8 hours versus 6.3 ± 2.2 hours for the lactone forms. Peak plasma concentrations for CPT-11 occur at the end of the infusion. The time to peak for SN-38 is highly inter-subject dependent occurring at variable time points 30 to 90 minutes after the end of infusion. Murine studies suggest that the liver may concentrate, convert CPT-11 to SN-38, and eliminate both compounds as well as the glucuronide conjugate of SN-38 (SN-38G) via biliary secretion. In rats, 55% of radiolabeled CPT-11 was excreted unchanged in the bile within 24 hours, while 21.7% was transformed to SN-38. It recently was demonstrated that plasma concentrations of SN-38G in subjects occur 0.5 to 3 hr after the SN38 peak and plasma levels generally exceeded that of SN-38. Overall, 73% of the radioactivity could be recovered from the feces of rats and 25% from the urine. Bile concentrations of CPT-11 were 10 to 60 fold higher than plasma concentrations in one subject during the first 6 hours following administration, while bile concentrations of SN-38 were 2 to 9 fold higher. Renal clearance has not been reported to be a major route of elimination for these compounds in humans.

